### 2. Purpose of the Study:

**1. Aim I – Clinical Trial Investigation.** In order to utilize Inhaled Epoprostenol (iEPO, Veletri®, Actelion Pharmaceuticals, South San Francisco, CA, USA) as an acceptable alternative to Nitric Oxide (iNO, INOMAX®, Mallinkrodt Pharmaceuticals, St. Louis, MO, USA) in adult patients, we propose a randomized, prospective, double-blinded trial in the cardiothoracic surgical population, which will evaluate the primary hypothesis that these two medications will have similar efficacy in pulmonary vasodilation and a similar impact on clinical outcomes in end-stage lung disease patients undergoing lung transplantation and end-stage heart failure patients under durable LVAD implantation or heart transplantation (Table 1).

**2. Aim II – Cost-Capture Analysis.** There will be a parallel prospective cost-capture analysis designed to precisely acquire the expenses that each drug incurs per patient averaged across all patients randomized to that drug.

### 3. Background & Significance:

**Introduction.** Inhaled Nitric Oxide (iNO) is a selective pulmonary vasodilator (PVD) with FDA-approval in the neonatal population alone. In adult patients, iNO is used off-label to treat pulmonary hypertension, right ventricular (RV) failure, and ventilation-to-perfusion mismatch. Adult patients who undergo durable LVAD implantation (e.g. Heartware®, Heartmate 2®, or Heartmate 3®) or cardiac transplantation for end-stage heart failure or those that have endured lung transplantation as a result of end-stage lung disease, compose the largest subpopulation which receives PVD therapy at Duke University Hospital. Intravenous Epoprostenol is FDA approved for adult patients with pulmonary hypertension and is the only agent which has displayed mortality benefit in these patients. The inhaled formulation of Epoprostenol (iEPO) was developed in order to maintain efficacy and avoid the systemic side effects of vasodilation and thrombocytopenia. Inhaled iEPO is used off-label in our cardiothoracic surgical patients for new-onset perioperative pulmonary arterial hypertension (PAH), known preoperative PAH, RV dysfunction with LVEF > 35-40%, and promotion of ventilation to perfusion matching through alveolar deposition of the prostanoid compound and vasodilation of the intimately associated intra-acinar pulmonary arteries. This vasodilation can decrease pulmonary vascular resistance and can improve oxygenation while avoiding systemic effects commonly seen in the intravenous formulation. iEPO has been introduced in the cardiothoracic operating rooms (OR) and ICU as a cost-conscious alternative medication to iNO. iEPO may display an equivalent efficacy profile to iNO for pulmonary vasodilation and oxygenation and have a similar impact on clinical outcomes. For the purposes of this writing, thoracic transplantation will refer to both heart and lung transplantation.

**Pharmacology.** There are 3 major pathways that affect pulmonary vascular tone: 1) Nitric oxide (vasodilatory), 2) Prostaglandin (vasodilatory), and 3) Endothelin (vasoconstrictive) pathways. During cardiothoracic operations, particularly transplantation and LVAD surgery, there is an appreciable imbalance in these pathways, which favors vasoconstriction. iNO administration, exerts its mechanism of pulmonary vasodilation and ventilation-to-perfusion matching through exogenous NO delivery and iEPO applies a similar mechanism via exogenous prostacyclin delivery. Both agents are delivered through mechanical ventilation to ventilated alveoli in order to promote gas exchange at the capillary bed. Both inhaled medications are desirable in this population due to pulmonary selectivity, absence of systemic vasodilation, as well as fast onset (5-10 seconds for iNO and 30-60 seconds for iEPO) and quick titration owing to short-half lives (10-20 seconds for iNO and 1-2 minutes for iEPO). There is no decision tree involved in the use of iNO vs iEPO except for that patient's known drug allergies which may preclude use of one inhaled agent in favor of the other. Of note, endothelin antagonists (e.g. bosentan), which are not part of our perioperative standard practice, are PO medications

**Table 1. Study Summary**

§Sample Size	N = 424 (50/50 by randomization strata)
Population	1. Lung transplantation (N = 200) 2. Heart Transplantation / LVAD implantation (N = 224)
Rationale	
 
• Comparison of iNO and iEpo impact on outcomes – evaluate for equivalency
 
• PVD therapy indications:               
 
1. Lung Transplant: Improvement of ventilator and perfusion matching after lung allograft implantation by vasodilation of ventilated pulmonary capillaries
 
2. Heart Transplant/LVAD Implantation: Improvement of RV contractility after cardiac allograft implantation or LVAD implantation by PVR reduction
 
 
 

Study Design	Prospective, Randomized, Double-Blinded
Primary Outcomes	1. Lung Transplant: Severe PGD (grade 3) 2a. Heart Transplant: RVAD insertion b. LVAD: INTERMACS Moderate or Severe RVF
Secondary Outcomes	All populations: 
 
• ICU LOS (days)
 
• Hospital LOS (days)
 
• Mechanical ventilator duration (hours)
 
• Postoperative AKI
 
• In-hospital mortality
 
• Mortality 30-day, 90-day, 1-year
 

Study length*	24-36 months

§Sample size powered for primary outcomes

\*Study length is determined through sample size divided by annual operations at Duke University Hospital; AKI = Acute kidney injury; iEpo = inhaled epoprostenol; iNO = Inhaled nitric oxide; ICU = Intensive care unit; LOS = Length of stay; LVAD = Left ventricular assist device; PGD = Primary graft dysfunction; PVD = Pulmonary vasodilators; PVR = Pulmonary vascular resistance; RVF = Right ventricular failure

## Research Summary – Inhaled Pulmonary Vasodilators in Thoracic Transplantation & LVAD Surgery

which require reliable gastrointestinal absorption that may not be present during high-dose inotropic support, and are not readily titrated to effect as are the inhaled PVD, iNO and iEPO.

**Contraindications and Adverse Effects.** Absolute indications for iNO in favor of iEPO are due to prostaglandin allergy leading to anaphylaxis (extremely rare) or if the patient is pregnant due to risk for labor induction as a result of prostacyclin agonism. Routine pregnancy testing is performed in the preoperative setting in line with established preoperative anesthesia testing criteria. Parturients rarely present for thoracic transplantation or LVAD implantation. There are no absolute contraindications to iNO therapy in adult patients but the iNO delivery device system routinely measures the toxic metabolite of iNO, nitrogen dioxide (NO2), which can lead to hypoxemia during metabolite accumulation. Additionally, methemoglobinemia (MetHb) is another rare adverse occurrence of prolonged iNO administration and MetHb levels are measured during arterial blood gas analysis.

**Preliminary retrospective study supporting noninferiority hypothesis.** In a retrospective study of 51 adult cardiothoracic surgical patients (all-comers, including thoracic transplantation, durable LVAD implantation, and non-transplant and non-LVAD cardiac surgical patients), requiring pulmonary vasodilation, our group illustrated similar efficacy between the use of iEPO and iNO with respect to optimizing RV hemodynamic variables,

including pulmonary vasodilation and mixed venous oxygenation (Table 2). During this investigation, iNO was initiated in the operating room (OR) and continued during transport and into the ICU. While in the ICU, postoperative hemodynamic stability was achieved within 2 hours and iNO was transitioned to iEPO over 30 minutes in order

**Table 2. Hemodynamic values in CT surgical patients comparing inhaled Nitric Oxide and Epoprostenol**

N= 51	*HR	†MAP	‡PAPs	§PAPd	¶PAPm	‡CVP	‡CI	PI	§LVAD flow	SVO2 (%)
iNO	98	78	37.9	18.6	25.3	12.5	2.61	5.36	4.66	71
iEpo	100	80	39.1	19.0	26.8	12.2	2.67	4.93	4.82	70
P-value	0.41	0.40	0.48	0.58	0.24	0.74	0.63	0.52	0.65	0.52

a = reported as mean values; \* units = beats per minute; † units = mm Hg; ‡ units = L/min/m^2

CI = Cardiac Index, CVP = Central Venous Pressure, HR = Heart Rate, iNO = Inhaled nitric oxide, iEpo = Inhaled epoprostenol, LVAD = Left Ventricular Assist Device, MAP = Mean Arterial Pressure, PAPs = Systolic Pulmonary Artery Pressure, PAPm = Mean Pulmonary Artery Pressure, PAPd = Diastolic Pulmonary Artery Pressure, PI = Pulsatility Index, SVO2 = Mixed Venous Oxygen Saturation

to provide continuous inhaled pulmonary vasodilation and allow the patient to self-control during medication cross-over between iNO and iEPO. Clinical variables were followed at 5-minute intervals for 1 hour after transition to iEPO. No statistically significant differences were seen in hemodynamic variables during this transition (Table 2). The small sample size and retrospective design, however, incorporated several confounding variables that could not be controlled and *prospective data was deemed necessary to achieve reliable conclusions by evaluating clinical outcomes in order to change clinician practice patterns*. Other investigations have demonstrated equivalence in hemodynamic variables, mixed venous oxygenation, and ventilation-to-perfusion matching when delivery of iNO was compared with iEPO. These studies were, however, also retrospective or inadequately powered to rely on conclusions related to outcome measures.

The large cost differential between these two agents remains an important concern for the health system: iNO is approximately 8-fold more expensive than iEPO, according to preliminary estimates based on PVD usage. Previous reports have estimated the cost of iNO administration to be between \$95.00 – \$115.00 per hour during medication delivery. The cost, however, has not precisely captured the time required to assemble the iNO delivery system as well as resources utilized to breakdown this setup into individual components following termination of delivery. The cost of iEPO delivery is captured at \$14.83 per hour, which includes solution compounding by pharmacy as well as processing for delivery and nebulization by respiratory care services. Additionally, the iEPO delivery-system setup is a one-time, fixed cost for the duration of administration. Similar secondary resource utilization capture for iEPO is required for accurate cost comparison between these two agents.

### 4. Design & Procedures:

#### Aim I – Development of a Definitive Clinical Trial Investigation.

**1. Randomization and Double-Blinding.** The clinical research unit (CRU) will receive preoperative notification of lung and heart transplantation patients by reviewing the transplant waitlist. Preoperative notification of LVAD implantation will be done by the review of the cardiothoracic surgical schedule. Using a 50% randomization process utilized and established by the CRU at Duke University Hospital, each eligible patient will be randomized to receive either iNO or iEPO. The primary endpoint data will be collected and documented in an electronic data capture system during the period of time the patient, clinical care team, and study team are blinded. Primary endpoint data collection will be complete prior to the subjects' discharge from the ICU, at which point the unblinding will occur. Since primary endpoint data collection will occur during the blinded period, the potential for bias will be substantially minimized.

**2. Measured Outcomes.** The primary endpoint for the comparison of efficacy in the Lung Transplant population will be the incidence of Grade 3 Primary Graft Dysfunction (PGD). This is defined by the International Society of Heart and Lung Transplantation (ISHLT) as severe hypoxemia with a PaO2-to-FiO2 ratio < 200 or the presence of venovenous extracorporeal membrane oxygenation (VV ECMO) at a time-point within the first 72

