## Research Summary – Inhaled Pulmonary Vasodilators in Thoracic Transplantation & LVAD Surgery

hours after lung transplantation. The primary endpoint for the comparison of efficacy in LVAD patients will be incidence of moderate or severe RV failure according to Interagency Registry for Mechanically Assisted Circulatory Support (INTERMACS) scoring. The primary endpoint for the comparison of efficacy in the heart transplant subset will be the incidence rate of RVAD insertion. Secondary endpoints related to clinical outcomes for all populations will be duration of postoperative mechanical ventilation, ICU Length of Stay (LOS), hospital LOS, incidence of acute kidney injury, incidence of in-hospital mortality, as well as postoperative mortality at 30-days, 90-days, and 1-year after operation (Table 1).

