### Subject Groups

Inhaled PVD therapy is administered to every patient undergoing thoracic transplantation and LVAD implantation at our institution and each patient is eligible for enrollment. Over a 3-year period (1 year for follow-up) we will prospectively enroll 200 lung transplant subjects and 224 heart transplant or LVAD implantation patients who will be informed and consented prior to their scheduled procedure. Potential subjects will be under the care of 1 or more investigators in this study. Consented subjects will be randomly assigned to 1 of 2 groups, iNO vs iEPO, to be initiated in the OR on the day of the operation based on accepted standard of practice and study protocol. Medication administration will be double-blinded, such that neither the surgical nor anesthesiology teams will be notified of the inhaled agent to which the patient has been randomized. Ability to unblind the delivery system will be made available to both teams if required to preserve optimal patient care. As per our standard practice, respiratory care services will manage the initiation and maintenance of inhaled PVDs in the OR and ICU, and these personnel will be the only practitioners notified of the actual delivered medication during study blinding.

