### Data Collection

*Secondary measures will be hemodynamic variables* (similar to those measured in Table 2) such as transesophageal echocardiographic (TEE) evaluation of RV function based on stand-of-practice protocol, intravenous administration of inotropes, serial measures of postoperative serum creatinine and GFR, resolution of elevated liver function tests (heart failure patients, illustrates improvement in RV function), incidence of thrombocytopenia (platelet count < 150 x 10^9/L) and trajectory of resolution, as well as ventilation-to-perfusion matching (arterial oxygen tension, PaO2; arterial carbon dioxide tension, PaCO2; and fraction of inspired oxygen, FiO2). Variables will be recorded at designated time points during the entire duration of administration – from initiation in the operating room to cessation in the ICU. These time points include: Intraoperative before surgical incision, time = 0 (initiation of PVD), 30 minutes, 2 hours, 6 hours, 12 hours, 18 hours, 24 hours, and every 6 hours up through 72 hours after initiation. These secondary measures will be obtained up through 72 hours after initiation regardless of cessation or continuation of the inhaled PVD. After 72 hours, increments of every 12 hours thereafter will be assessed if PVD administration continues. Ventilation and perfusion nuclear scans will be obtained and recorded per standard clinical practice for each group of lung transplant recipients. Established protocols with criteria for initiation of medication weaning have been created according to each medication based on individual pharmacokinetic properties. Once established criteria are met, weaning of each inhaled PVD will begin and continue until the medication is terminated according to standardized weaning protocols established for lung transplant patients and heart transplant/LVAD patients.

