*Subject follow up.* Subject will be contacted by phone by a member of the research team and be asked a short series of questions to assess their current medical condition and any changes since surgery at 30-days (± 3 days), 90-days (± 5 days), and 1-year (± 7 days) after surgery completion date. The phone follow-up should take approximately 5 minutes of the subject's time. If subjects have been admitted to a hospital outside of Duke Health after surgery they will be asked to sign an authorization of release to provide us permission to obtain medical information related to their hospitalization.

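### Tying both unblinding and the end of primary-endpoint collection to ICU discharge leaves RVAD insertion (and possibly RV failure) without a fixed window and opens the code before hospital LOS and follow-up are complete

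*Combined protocol and SAP*

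**What the plan says.** Section 4, Aim I (Randomization and Double-Blinding) has primary-endpoint data recorded "during the period of time the patient, clinical care team, and study team are blinded". It then states that "Primary endpoint data collection will be complete prior to the subjects' discharge from the ICU", and it ties the opening of the code to that same event: "discharge from the ICU, at which point the unblinding will occur". The bias argument there is made for the primary endpoint only.

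Measured Outcomes gives the three primary endpoints. Grade 3 PGD in lung transplant is judged "at a time-point within the first 72" "hours after lung transplantation". RVAD insertion in heart transplant has no stated window. Moderate or severe RV failure in LVAD patients is judged by INTERMACS scoring, which is not reproduced. The secondary outcomes are ventilation duration, ICU LOS, hospital LOS, AKI, in-hospital mortality, and mortality at 30 days, 90 days and 1 year.

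Under Data Collection, variables are recorded over the period of drug administration, "from initiation in the operating room to cessation in the ICU". Secondary measures, including PaO2 and FiO2, continue to 72 hours after initiation whether or not the drug is still running. For the 30-day, 90-day and 1-year contacts, "Subject will be contacted by phone by a member of the research team".

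Subject Groups names respiratory care services as the unblinded staff ("these personnel will be the only practitioners notified of the actual delivered medication during study blinding") and lets the surgical and anesthesiology teams unblind for patient care.

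**The concern.** Two different things are attached to one event whose timing varies by patient and may depend on treatment.

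The first is observation time. If an endpoint is counted only until ICU discharge, and one drug shortens the ICU stay, that arm has less time in which an event can be counted. The comparison then mixes the drug's effect on the event with its effect on ICU stay. The heart transplant/LVAD stratum is 224 of the 424 planned patients.

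The second is the blind. Once the code is open, allocation can influence decisions that involve judgement: when to send the patient home, how closely to look for kidney injury after the ICU, and how the follow-up questions are put. Losses shared by both arms matter too. Section 11 reads a non-significant difference as equivalence, and if the same share of events is missed in each arm, the difference shrinks by that share. The error then runs toward the conclusion the trial hopes to reach.

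**Working it through.** No stated figure in the plan depends on the unblinding time, so there is nothing to reproduce. The check sets each outcome's window against ICU discharge.

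**1. RVAD insertion and RV failure.**
- The only limit the text places on counting RVAD insertion is the end of collection before ICU discharge.
- With a roughly constant low event rate h per day and mean ICU stays L1 and L2, the counted incidences are about h × L1 and h × L2. Even with identical h, they differ by h × (L1 − L2).
- The documents give neither h nor the ICU stays, so no number can be put in. The difference is zero only if ICU stay does not differ by arm or no events fall after discharge.
- Events on ICU readmission have no stated place.
- For RV failure the same follows only if INTERMACS scoring has no time rule of its own. If it has one, that rule and the ICU cut-off must be reconciled.

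**2. Grade 3 PGD.** Let T be the hours from transplantation to ICU discharge.
- T ≥ 72: the window has closed before the code opens, and there is no problem.
- T < 72: either collection stops at T and 72 − T hours go unobserved, or it continues with the code open.
- No section requires 72 hours in the ICU or says what happens on earlier discharge. The share of patients with T < 72 is unknown.

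Illustration, using the section 11 rate of 0.35 and margin of 0.19. The missed shares are assumptions.

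| Share of PGD events missed | Bias if one arm only | Share of margin | Counted rate if both arms |
|---|---|---|---|
| 2% | 0.35 × 0.02 = 0.007 | 0.007 / 0.19 = 4% | 0.343 |
| 5% | 0.35 × 0.05 = 0.0175 | 0.0175 / 0.19 = 9% | 0.3325 |
| 10% | 0.35 × 0.10 = 0.035 | 0.035 / 0.19 = 18% | 0.315 |

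**3. The 72-hour measurement schedule.** From time 0 there are 15 time points: 0, 0.5, 2, 6, 12, 18 and 24 hours (7), then every 6 hours from 30 to 72 (8). If ICU discharge came 48 hours after initiation (assumption), 4 would follow unblinding (54, 60, 66, 72). At 60 hours, 2 would.

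**4. Secondary outcomes in a patient leaving the ICU alive.**
- Settled at or normally before unblinding: ventilation duration and ICU LOS.
- Completed later: hospital LOS, in-hospital death, and death at 30 days, 90 days and 1 year.
- AKI has no stated window and may fall on either side.
- Counting each mortality time separately, 5 of 8 finish later (62.5%). By Table 1 bullets it is 3 of 6, or 4 of 6 if AKI runs past the ICU. Four of the five are deaths.

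**5. Need for early unblinding.** Drug delivery is described as ending in the ICU, respiratory care already knows the drug and documents resource use for Aim II, and clinical-need unblinding exists. Neither delivery nor cost capture requires the code to be opened to others at ICU discharge.

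**The case against.** A reader might infer that the plan intends to open the code before grade 3 PGD has been collected. The documents do not support that. The sentence on unblinding begins by saying primary collection is complete by then, and the schedule already takes PaO2 and FiO2 to 72 hours regardless of drug cessation. The endpoint also rests on a blood-gas ratio or VV ECMO, which leaves little to judgement. What stands is narrower. Completeness is asserted without a rule for early discharge, the schedule does not mention ICU discharge, and its clock starts at drug initiation rather than at transplantation.

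A reader might also infer that most secondary outcomes are compromised. The majority depends on counting each mortality time separately, and knowing the allocation does not readily misclassify a death. ICU LOS is determined under blinding. Serial creatinine is scheduled to 72 hours, so the AKI concern is limited to later work-up. The plan claims bias protection only for the primary endpoint, so it does not contradict itself, and it does not say who is told the assignment. That the whole team and the callers are then unblinded is the natural reading, because these are the groups said to be blinded until then, but it remains an inference.

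Finally, a missing window is an endpoint-definition gap that would exist whenever the code was opened, and INTERMACS scoring may close it for LVAD patients. Both points are fair. The gap belongs here because the ICU-discharge cut-off is what turns an unstated window into one that varies by patient.

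**Conclusion.** The concern holds in limited form and should be corrected. It is clearest for RVAD insertion, where the counted period is the patient's own ICU stay. For RV failure it is conditional on what INTERMACS scoring specifies. For grade 3 PGD it is a possibility of unknown frequency, softened by the existing blood-gas schedule; under the assumed 2% to 10% one-arm loss it uses 4% to 18% of the margin. Among secondary outcomes the real exposure is hospital LOS, post-ICU AKI and the follow-up calls, not mortality.

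Bias between arms in the observation-time part requires that ICU stay differ by drug and that some events fall after discharge. The documents neither show nor exclude either. The conclusion rests on the plain reading that the patient, care team and study team stop being blinded at ICU discharge.

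**What to change.** 1. In section 4 (Randomization and Double-Blinding), set routine unblinding of the patient, care team, outcome assessors and follow-up callers no earlier than the later of hospital discharge and completion of the primary-endpoint window. Preferably keep assessors and callers blinded through the 1-year contact. Leave the clinical-need unblinding in Subject Groups unchanged.

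2. In Measured Outcomes, give each primary endpoint one fixed window, the same for both arms and regardless of ICU discharge or readmission. Collect grade 3 PGD to 72 hours after transplantation in every lung patient. Collect RVAD insertion and RV failure to a prespecified fixed time consistent with the INTERMACS definition, and state that time in the protocol. Take these from the medical record. The 30-day contact is a phone call of about 5 minutes, and nothing shows that it can score RV failure.

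The cost is protocol wording, later disclosure of assignments and some post-ICU chart review. The principal investigator's adverse-event relatedness review (section 12) would also be done blinded for longer, unless unblinding is clinically needed; the protocol should say how that works, since it lists expected effects separately by drug.
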